9.2 Discussion of Study Design, Including Choice of Control Group

Study 270-301 is designed to be a Phase 3, single-arm, open-label study in hemophilia A patients with residual FVIII levels ≤ 1 IU/dL previously treated with prophylactic exogenous FVIII. Hemophilia A patients who provide written informed consent, meet the entry criteria definition of residual FVIII activity, have well-documented historical data for the previous 12 months concerning exogenous FVIII usage and bleeding episodes, and do not have antibodies to AAV5 will be eligible to enroll in the study.

Approximately 70 subjects will be enrolled at the 6E13 vg/kg BMN 270 dose. Subjects will be followed for 52 weeks post-BMN 270 infusion during which safety and efficacy assessments will be taken. After the final analysis at 52 weeks post-infusion, safety and efficacy will then continue to be assessed long-term for approximately a total of 5 years. During enrollment, the DMC will review available safety and efficacy data on an ongoing basis and may decide to recommend dosing subjects at a different dose level (not to exceed 6E13 vg/kg) based on emerging data from 270-301 and their overall benefit:risk assessment.

Study 270-301 is a self-controlled study. Parameters for each subject will be compared to a pre-treatment assessment of safety (liver function) and efficacy (number of bleeds, use of FVIII replacement therapy).

9.3 Selection of Study Population

Approximately 70 adult hemophilia A patients with residual FVIII levels \leq 1 IU/dL may enroll into the study.

Additional criteria for participation in the study are provided in Section 9.3.1 and Section 9.3.2.

9.3.1 Inclusion Criteria

Individuals eligible to participate in this study must meet all of the following inclusion criteria:

- 1. Males \geq 18 years of age with hemophilia A and residual FVIII levels \leq 1 IU/dL as evidenced by medical history, at the time of signing the informed consent.
- 2. Must have been on prophylactic FVIII replacement therapy for at least 12 months prior to study entry. High-quality, well-documented historical data concerning bleeding episodes and FVIII usage over the previous 12 months must be available.
- 3. Treated/exposed to FVIII concentrates or cryoprecipitate for a minimum of 150 exposure days (EDs).

Page 51

- 4. Willing and able to provide written, signed informed consent after the nature of the study has been explained and prior to any study-related procedures.
- 5. No history of FVIII inhibitor, and results from a Bethesda assay with Nijmegen modification of less than 0.6 Bethesda Units (BU) on 2 consecutive occasions (the most recent one of which should be tested at the central laboratory) at least one week apart within the past 12 months
- 6. Sexually active participants must agree to use an acceptable method of effective contraception--double barrier contraception (ie, condom + diaphragm; or condom or diaphragm + spermicidal gel or foam) or their female partner either using hormonal contraceptives or having an intrauterine device--for at least 6 months post-infusion. After 6 months, subjects may stop contraception use only if they have had 3 consecutive semen samples with no detectable viral vector DNA.
- 7. Willing to abstain from alcohol consumption for at least the first 52 weeks following BMN 270 infusion.
- 8. HIV positive patients may be enrolled, only if the patient has a CD4 count > 200/mm³ and an undetectable viral load.

9.3.2 Exclusion Criteria

Individuals who meet any of the following exclusion criteria will not be eligible to participate in the study:

- 1. Detectable pre-existing antibodies to the AAV5 capsid.
- 2. Any evidence of active infection or any immunosuppressive disorder, except for HIV infection as described in the inclusion criterion above.
- 3. Significant liver dysfunction with any of the following abnormal laboratory results:
 - ALT (alanine transaminase) or AST >2X ULN;
 - Total bilirubin >2X ULN;
 - Alkaline phosphatase >2X ULN; or
 - INR (international normalized ratio) ≥ 1.4 .

Subjects whose liver laboratory assessments fall outside of these ranges may undergo repeat testing and, if eligibility criteria are met on retest, may be enrolled after confirmation by the Medical Monitor. In addition, subjects with abnormal laboratory results related to confirmed benign liver conditions (eg, Gilbert's syndrome) are considered eligible for the study notwithstanding their abnormal laboratory results and may be enrolled after discussion with the Medical Monitor.

4. Prior liver biopsy showing significant fibrosis of 3 or 4 as rated on a scale of 0-4 on the Batts-Ludwig (Batts 1995) or METAVIR (Bedossa 1996) scoring systems, or an equivalent grade of fibrosis if an alternative scale is used.

Page 52

- 5. Evidence of any bleeding disorder not related to hemophilia A.
- 6. Platelet count of $< 100 \times 10^9/L$.
- 7. Creatinine $\geq 1.5 \text{ mg/dL}$.
- 8. Liver cirrhosis of any etiology as assessed by liver ultrasound.
- 9. Chronic or active hepatitis B as evidenced by positive serology testing and confirmatory HBV DNA testing. Refer to the Centers for Disease Control (CDC) table for the interpretation of serological test results in the Laboratory Manual.
- 10. Active Hepatitis C as evidenced by detectable HCV RNA or currently on antiviral therapy.
- 11. Active malignancy, except non-melanoma skin cancer.
- 12. History of hepatic malignancy.
- 13. History of arterial or venous thromboembolic events (eg, deep vein thrombosis, non-hemorrhagic stroke, pulmonary embolism, myocardial infarction, arterial embolus), with the exception of catheter-associated thrombosis for which anti-thrombotic treatment is not currently ongoing.
- 14. Known inherited or acquired thrombophilia, including conditions associated with increased thromboembolic risk, such as atrial fibrillation.
- 15. Treatment with any investigational product within 30 days or 5 half-lives of the investigational product prior to the screening period. For subjects who have received a prior investigational product, all ongoing adverse events (AEs) experienced while receiving that investigational product must have resolved prior to screening for this study.
- 16. Any condition that, in the opinion of the Investigator or Sponsor would prevent the patient from fully complying with the requirements of the study (including possible corticosteroid treatment outlined in the protocol) and/or would impact or interfere with evaluation and interpretation of subject safety or efficacy result.
- 17. Prior treatment with any vector or gene transfer agent.
- 18. Major surgery planned in the 52-week period following the infusion with BMN 270.
- 19. Use of systemic immunosuppressive agents, not including corticosteroids, or live vaccines within 30 days before the BMN 270 infusion.
- 20. Concurrent enrollment in another clinical study, unless it is an observational (non-interventional) clinical study that does not interfere with the requirements of the current protocol or have the potential to impact the evaluation of efficacy and safety of BMN 270 and with prior consultation with the Medical Monitor.
- 21. Known allergy or hypersensitivity to BMN 270 investigational product formulation.

Page 53

22. Unwilling to receive blood or blood products for treatment of an adverse event and/or a bleeding episode.

9.3.3 Removal of Subjects from Treatment or Assessment

Subjects may withdraw their consent to participate in the study at any time without prejudice. The Investigator must withdraw from the study any subject who requests to be withdrawn. Such subjects will always be asked about the reason(s) for withdrawal. The Investigator will discuss with the subject appropriate procedures for withdrawal from the study. The Investigator should ask the subject's consent to perform the procedures listed under the early termination visit. Should a subject withdraw from the study, all efforts will be made to complete and report the observations as thoroughly as possible up to the date of the withdrawal.

A subject's participation in the study may be discontinued at any time at the discretion of BioMarin or of the Investigator and in accordance with his/her clinical judgment. When possible, the tests and evaluations listed for the termination visit should be carried out and every effort will be made to gather follow-up safety data if possible.

BioMarin must be notified of all subject withdrawals as soon as possible. BioMarin also reserves the right to discontinue the study at any time for either clinical or administrative reasons and to discontinue participation by an individual Investigator or site for poor enrollment or noncompliance.

Reasons for which the Investigator or BioMarin may withdraw a subject from the study include, but are not limited to, the following:

- Subject requires medication or medical procedure prohibited by the protocol
- Subject does not adhere to study requirements specified in the protocol
- Subject was erroneously enrolled into the study or does not meet entry criteria and not yet been dosed with BMN 270; subjects who do not meet entry criteria but who erroneously receive BMN 270 should remain in the study for safety monitoring
- Subject is lost to follow-up

If a subject fails to return for scheduled visits, a documented effort must be made to determine the reason. If the subject cannot be reached by telephone, a certified letter should be sent to the subject requesting contact with the Investigator. This information should be recorded in the study records.

The Investigator or designee must explain to each subject, before enrollment into the study, that for evaluation of study results, the subject's protected health information obtained during

Page 54

the study may be shared with the study Sponsor, regulatory agencies, and IRB/IEC/REB. It is the Investigator's (or designee's) responsibility to obtain written permission to use protected health information per country-specific regulations, such as the Health Insurance Portability and Accountability Act (HIPAA) in the US, from each subject. If permission to use protected health information is withdrawn, it is the Investigator's responsibility to obtain a written request, to ensure that no further data will be collected from the subject and the subject will be removed from the study.

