9.3.4 Subject Identification and Replacement of Subjects

Each subject will be assigned a unique subject identifier. This unique identifier will be on all eCRF pages. In legal jurisdictions where use of initials is not permitted, a substitute identifier will be used.

Subjects who withdraw from the study after receiving BMN 270 will not be replaced.

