9.4.8 Prior and Concomitant Medications

All prescription and over-the-counter medications (including dietary and herbal supplements) taken by a subject for 30 days before Screening will be recorded on the designated eCRF. The Investigator may prescribe additional medications, deemed necessary to provide adequate prophylactic or supportive care, during the study, as long as the prescribed medication is not prohibited by the protocol. In the event of an emergency, any needed medications may be prescribed without prior approval, but the Medical Monitor must be notified of the use of any contraindicated medications immediately thereafter. Any concomitant medications added or discontinued during the study should be recorded on the eCRF. Medications should, whenever possible, not be recorded in the electronic database with a frequency of PRN.

The following medications are prohibited starting 30 days before Screening and through the end of the study, and the Sponsor must be notified if a subject receives any of these during the study:

- Any investigational therapy
- Systemic immunosuppressive agents, except for corticosteroids
- Emicizumab
- Fitusiran
- Concizumab

The following medications should be avoided, starting 30 days prior to and for at least 52 weeks after BMN 270 infusion and minimized throughout the remaining duration of the study.

- Alcohol
- Herbal and natural remedies and dietary supplements
- Medications which may be hepatotoxic

Page 58

Vaccines should also be avoided during this period, but in particular during the first 26 weeks unless clinically indicated.

The following medications should be avoided during oral corticosteroid therapy:

- Vaccines
- NSAIDs

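### Section 9.3.3 permits already-infused subjects to be withdrawn for needing a prohibited medication or for non-adherence, after which bleed, FVIII-use and FVIII-activity data are no longer required

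*Protocol*

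**What the plan says.** Section 9.3.3 (Amendment 1; the original protocol has the same list) opens its list permissively and leaves it open-ended: "Reasons for which the Investigator or BioMarin may withdraw a subject from the study include, but are not limited to, the following". Two of the listed reasons are "Subject requires medication or medical procedure prohibited by the protocol" and "Subject does not adhere to study requirements specified in the protocol". Neither depends on whether the subject has been infused. The third reason, erroneous enrollment, does: it applies before dosing, and "subjects who do not meet entry criteria but who erroneously receive BMN 270 should remain in the study for safety monitoring".

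For discretionary discontinuation, the same section asks for the termination-visit assessments when possible and adds that "every effort will be made to gather follow-up safety data if possible". It does not mention efficacy data. Under Section 9.3.4, "Subjects who withdraw from the study after receiving BMN 270 will not be replaced".

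Section 9.4.8 sets the duration of the prohibition: "The following medications are prohibited starting 30 days before Screening and through the end of the study". The Amendment 1 list contains investigational therapy, systemic immunosuppressants other than corticosteroids, emicizumab, fitusiran and concizumab. The consequence that section attaches to their use is notification of the sponsor.

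Section 9.1 plans long-term safety and efficacy assessment of all subjects for about 5 years in total, and Section 8 makes long-term safety an objective.

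**The concern.** The treatment is given once and cannot be stopped. After Day 1, withdrawal takes away nothing but follow-up. The protocol accepts this logic for wrongly enrolled subjects who were infused, but does not apply it to the two other reasons.

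One of those reasons can be triggered by the outcome itself. A subject who loses response and moves to a listed hemophilia agent, or who is given a non-corticosteroid immunosuppressant for a liver-enzyme elevation, meets it because of how the treatment turned out. In a single-arm, self-controlled trial there is no comparator in which similar losses could offset this. If such subjects are removed, the remaining data on annualized bleeding rate (ABR), FVIII use and FVIII activity come disproportionately from those who did well, and the long-term safety record thins where it may be most informative.

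**Working it through.** The documents give no rate for these withdrawals. The main check is therefore a reading of the text. The arithmetic only shows what can be said about size.

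**1. Do the reasons reach infused subjects?** Yes. The third reason in Section 9.3.3 separates infused from not-yet-infused subjects; the first two do not.

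**2. Which routes lead there?**
- Loss of response, then FVIII prophylaxis resumed: foreseen in Sections 9.1 and 9.7.2.1 and not on the Section 9.4.8 list. The first reason is not met.
- A switch to a listed hemophilia agent, or use of a non-corticosteroid systemic immunosuppressant: the first reason is met.
- Missed requirements: the second reason is met, whatever the outcome.

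**3. What is still collected after removal?**
- One termination visit, with as many assessments as possible (Section 12.8).
- Safety data on a best-effort basis (Section 9.3.3), and reported adverse events followed to resolution or stabilization (Section 10.6).
- Later deaths and serious events only if the investigator thinks they may be related; cancer, or a congenital anomaly in offspring, if the investigator learns of it (Section 10.7).
- Bleeds, FVIII use, FVIII activity and scheduled liver tests: no requirement.

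**4. Does the analysis text close the gap?** Section 14.7 defines the efficacy set as everyone infused, and Section 14.1.2 promises missing-data sensitivity analyses for the primary endpoint. The first keeps a subject in the set but supplies no observations. The second does not name ABR or FVIII use. Further handling may be in the SAP, but no SAP can recover bleeds or liver tests that were never recorded.

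**5. The plan's own power figures (Section 14.6).** With N = 70, effect size 0.6 and 2-sided alpha 0.025, the noncentrality is 0.6 × √70 = 5.02. The noncentral t distribution gives 99.6% power, consistent with the stated minimum of 95%. For ABR, a change of 1 − 3.5 = −2.5 with about 90% superiority power implies an SD of change of about 5.8 (not stated in Amendment 1). If 14 of 70 subjects contribute no data (n = 56), power is 98.4% for the primary endpoint and about 81% for ABR superiority. Loss of numbers is not the main issue; selection is.

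**6. Can the bias be sized?** Assume that k removed subjects contribute nothing, that the 70 − k retained average the planned change of −2.5, that removed subjects would have had ABR x, and that only completers are analyzed. The analysis then shows −2.5, while the mean over all infused is [(70 − k)(−2.5) + k(x − 3.5)] / 70.

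| k | x = 3.5 (no change) | x = 18 |
|---|---|---|
| 4 | −165/70 = −2.36 | (−165 + 58)/70 = −1.53 |
| 7 | −157.5/70 = −2.25 | (−157.5 + 101.5)/70 = −0.80 |
| 14 | −140/70 = −2.00 | (−140 + 203)/70 = +0.90 |

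The value 18 is the upper end of the retrospective on-demand median ABRs in Section 7.3, used here as if it were a mean. The overstatement runs from 2.50 − 2.36 = 0.14 to 2.50 + 0.90 = 3.4 bleeds per year. Neither k, nor x, nor the completers-only rule comes from the plan. The width of the range shows that the size cannot be determined; the figures are not an estimate.

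**The case against.** A reader might infer that treatment failures leave follow-up. The text does not say so. The verb in Section 9.3.3 is permissive, and Section 9.4.8 asks only for notification and lets needed medication be given in an emergency with notification afterwards. Both fit with a subject staying in. The foreseen route after loss of response is a discussion about resuming FVIII prophylaxis, which triggers no prohibited-medication reason. All of this stands, and it limits the point to subjects who receive a listed agent or do not adhere.

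A reader might also infer a computable inflation of efficacy, for example by dividing the mean FVIII change by one minus the withdrawn fraction and using the original protocol's 15% discontinuation rate. That would require every withdrawn subject to be a failure with zero change and to be dropped without imputation. The 15% was an all-cause allowance, and Amendment 1 deleted it. No such figure is supported.

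Nor do the documents support saying that long-term safety data are simply lost: the termination visit, the best-effort clause and related-event reporting remain. They are partial, however, and none requires scheduled liver tests, bleeds or FVIII use.

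The note to file describes 2-year analysis rules for FVIII prophylaxis used after infusion and for immunosuppression classed as either CS or AIS. This suggests that at least some such subjects were still observed, though it does not show what Amendment 1 required.

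Retention alone is also not a full remedy. Amendment 1 itself says that the added hemophilia agents could affect the assessment of FVIII levels, and bleeds prevented by another agent would be credited to BMN 270. That objection stands, and the fix has to deal with it.

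**Conclusion.** The concern holds as a permission that fits the design badly. Infused subjects can be taken out of the study for a reason that may follow from a poor outcome, they are not replaced, and after removal efficacy data are not required and safety data are best-effort. This conflicts with the commitment to follow all subjects for about 5 years. The likely direction of any bias in ABR, FVIII use and FVIII activity favors BMN 270. Its size depends on how often the permission is used, on the outcomes of those removed and on missing-data handling, none of which this document fixes.

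The conclusion rests on Section 9.3.3 of the original protocol and Amendment 1. The corresponding text of Amendment 2 and later versions was not in the part available, so a later correction cannot be excluded. No view is taken on which medications should be prohibited.

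**What to change.** Extend the existing retention clause in Section 9.3.3. An infused subject who needs a prohibited medication or procedure, or who does not adhere, remains in scheduled safety, bleeding, FVIII-use and FVIII-activity follow-up unless he withdraws consent, is lost to follow-up or transfers to another BMN 270 study (a route that Section 12.9 already recognizes). Record the medication and its start date. Flag FVIII values and bleeds observed on another hemostatic agent so that they are not credited to BMN 270. Check first whether a later amendment already does this.

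The cost is a few sentences of amendment text, continued visits for a few subjects, and some flagged data that will not yield a clean Weeks 49-52 value. The change alters what is observed, not how any subject is treated.

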9.3.3.1 Study Safety Evaluation Criteria

If any of the following events occur in a subject in the study who has received BMN 270 infusion, an urgent evaluation by the DMC will be required and further enrollment into the trial will be temporarily put on hold if recommended by the DMC per Section 9.1.

- 1. Liver dysfunction (criteria do not apply to ALT elevations with an extra-hepatic etiology):
 - \circ ALT >5x ULN, for more than 2 weeks
 - o ALT >3x ULN and (total bilirubin >2x ULN or INR >1.5)
 - o ALT >3x ULN with signs and symptoms of liver dysfunction
- 2. The occurrence of Grade 4 or Grade 5 adverse events assessed as related to study drug (events of liver dysfunction are defined above).
- 3. The occurrence of an AE of hepatic failure.
- 4. The detection of high-titer neutralizing antibodies (>5 BU) to hFVIII following BMN 270 infusion in two subjects.
- 5. The occurrence of any cancer (except non-melanoma skin cancer) at any point after BMN 270 infusion.
- 6. The occurrence of a thromboembolic event with FVIII activity > 150 IU/dL in one subject.

If any of the following events occurs in a subject in the study who has received BMN 270 infusion, an urgent evaluation by the DMC will be required. Further enrollment into the trial will continue while DMC evaluation is ongoing, unless deemed otherwise by the DMC:

- 1. The detection of high-titer neutralizing antibodies (>5 BU) to hFVIII following BMN 270 infusion in one subject.
- 2. Occurrence of a thromboembolic event in one subject.

Page 55

9.3.4 Subject Identification and Replacement of Subjects

Each subject will be assigned a unique subject identifier. This unique identifier will be on all eCRF pages. In legal jurisdictions where use of initials is not permitted, a substitute identifier will be used.

Subjects who withdraw from the study after receiving BMN 270 will not be replaced.

9.3.5 Duration of Subject Participation

The duration of participation for each subject will be approximately 264 weeks. This includes 4 weeks of screening, 1 day of BMN 270 infusion, 52 weeks of Post-Infusion Follow-Up, and 208 weeks of Long-Term Follow-Up.

9.4 Treatments

9.4.1 Treatments Administered

BioMarin and/or its designee will provide the study site with a supply of IP sufficient for the completion of the study. BioMarin is responsible for shipping study drug to clinical sites.

